11.9 Urgent Safety Measures

The PI or designee may take appropriate urgent safety measures in order to protect participants from any immediate hazards to their health or safety. The main REC will be notified by telephone immediately and in writing within three working days (by the CI or sponsor). The written notification should set out the reasons for the urgent safety measures and the plan for further action.

11.10 Data Monitoring

11.10.1 Data access

Prior to commencement of the study, the PI at each site will give permission for trial related monitoring, audits, ethics committee review and regulatory inspections, by providing direct access to source data and trial related documentation. Consent from participants for direct access to data will also be obtained. The participants' confidentiality will be maintained and will not be made publicly available to the extent permitted by the applicable laws and regulations.

11.10.2 Monitoring arrangements

The CTU will be responsible for trial monitoring. On-site monitoring visits will be conducted in accordance with the trial monitoring plan. On-site monitoring will be an on-going activity from the time of initiation until trial close-out and will comply with the principles of Good Clinical Practice (GCP). The frequency and type of monitoring will be detailed in the monitoring plan and agreed by the trial Sponsor.

Before the trial starts at a participating site, a site initiation process will be completed to ensure that all relevant essential documents and trial supplies are in place and that site staff are fully aware of

the trial protocol and procedures. On-site monitoring visits during the trial will check the accuracy of entries on CRF's against the source documents, the adherence to the protocol, procedures and GCP, and the progress of participant recruitment and follow up.

The PI or designee should ensure that access to all trial related documents including source documents (to confirm their consistency with CRF entries) are available during monitoring visits. The extent of source data verification (SDV) will be documented in the monitoring plan.

The close out procedure at each site will commence once the final participant enrolled has completed all follow-up required by the protocol.

12 REGULATIONS, ETHICS AND GOVERNANCE

The trial will comply with the principles of GCP and the Research Governance Framework.

12.1 Sponsorship

The BHSCT will act as Sponsor for the study and the CI will take overall responsibility for the conduct of the trial. Separate agreements will be put in place between the Sponsor, CI and each organisation who will undertake Sponsor delegation duties in relation to the management of the study.

12.2 Regulatory and Ethical Approvals

The trial will be conducted in accordance with the ethical principles that have their origin in the Declaration of Helsinki. The protocol will be approved by a Research Ethics Committee.

12.3 Protocol Amendments

The investigators will conduct the study in compliance with the protocol given approval/favourable opinion by the Ethics Committee. Changes to the protocol may require ethics committee approval/favourable opinion prior to implementation, except when modification is needed to eliminate an immediate hazard(s) to participants. The CTU in collaboration with the CI and sponsor will submit all protocol modifications to the research ethics committees for review in accordance with the governing regulations. Amendments to protocol will be communicated to sites by the CTU in collaboration with the CI. Protocol compliance will be monitored by the CTU who will undertake monitoring visits to ensure that the trial protocol is adhered to and that necessary paperwork (e.g. CRF's, participant consent) is being completed appropriately.

12.4 Good Clinical Practice

The trial will be carried out in accordance with the principles of the International Conference on Harmonisation Good Clinical Practice (ICH-GCP) guidelines (www.ich.org). All members of the trial team will be required to have GCP training.

12.5 Protocol Compliance

A protocol deviation is defined as an incident which deviates from the normal expectation of a particular part of the trial process. Any deviations from the protocol will be fully documented on the protocol deviation form in the CRF. A serious breach is defined as a deviation from the trial protocol or GCP which is likely to effect to a significant degree:

- (a) the safety or physical or mental integrity of the subjects of the trial; or
- (b) the scientific value of the trial

The PI or designee is responsible for ensuring that serious breaches are reported directly to the Sponsor within one working day of becoming aware of the breach. Protocol compliance will be monitored by the CTU who will undertake site visits to ensure that the trial protocol is adhered to and that necessary paperwork (e.g. CRF's, participant consent) is being completed appropriately.

12.6 Participant Confidentiality

In order to maintain confidentiality, all CRF's, questionnaires, study reports and communication regarding the study will identify the participants by the assigned unique trial identifier only. Databases where information will be stored will be password protected. Participant confidentiality will be maintained at every stage and will not be made publicly available to the extent permitted by the applicable laws and regulations.

12.7 Post-trial Care

There are no specific post-trial provisions for participants.

12.8 Indemnity

The BHSCT will provide indemnity for any negligent harm caused to participants by the design of the research protocol through the Clinical Negligence Fund in Northern Ireland.

12.9 Data Access

Following the publication of the primary and secondary study outcomes, there may be scope for the CI in the study to conduct additional analyses on the data collected. In such instances the CI will discuss this with the TMG. In the event of publications arising from such analyses, those responsible will need to provide the CI with a copy of any intended manuscript for approval prior to submission. Authorship will need to take the format of "[name] on behalf of the MIRROR Clinical Trial Group" or something similar which will be agreed by the TMG.

12.10 Record Retention

Archiving of essential documents will take place as outlined in the Sponsor delegation framework. The PI will be provided with an ISF by the CTU and will maintain all trial records according to GCP and the applicable regulatory requirements. The PI is responsible for archiving of essential documents at local sites in accordance with the requirements of the Sponsor and local policies. The PI has a responsibility to allow Sponsor access to archived data and can be audited by the Sponsor or competent authority on request. The Trial Master File (TMF) will be held by the CTU within the BHSCT and the essential documents that make up the TMF are listed in an SOP. On completion of the trial, the TMF and study data will be archived by the CTU according to the applicable regulatory requirements and for up to five years as required by the BHSCT Sponsor. Following confirmation from the Sponsor, the CTU will notify the PI when they are no longer required to maintain the files. If the PI withdraws from the responsibility of keeping the trial records, custody must be transferred to a person willing to accept responsibility and this must be documented in writing to the CTU and Sponsor. Images stored in CARF will be archived according to the applicable regulatory requirements at the request of the CI.

12.11 Competing Interests

The research costs including the cost of the intervention were funded by NIHR EME. The CI and members of the TMG have no financial or non-financial competing interests and the members of the DMEC/TSC will be asked to confirm that they have no conflict of interest. In the event that a DMEC/TSC member reports a conflict of interest, advice will be sought from the Sponsor.

13 DISSEMINATION/PUBLICATIONS

13.1 Publication Policy

The final study report will be provided by the Trial Statistician; it is anticipated that the study findings will be published in national and international peer review journals which will be led by the CI. Publications will be discussed at the TMG and will be considered on a case by case basis. This will secure a searchable compendium of these publications and make the results readily accessible to the public and health care professionals. In addition, study findings may be presented at both national and international meetings and also to appropriate participant groups. NIHR will be acknowledged as the funder in research publications and a copy of papers will be sent to the relevant co-ordinating centre 28 days before publication.

Due to limited resources, it will not be possible to provide each participant with a personal copy of the results of the trial. However upon request, participants involved in the trial will be provided with a lay summary of the principal study findings. The most significant results will be communicated to the public through press releases. An on-going update of the trial will also be provided on the NICTU website.

The project will have a dedicated website providing details on the study and the research team members will provide regular updates on study progress. We plan to publish our trial protocol in accordance with the open access policies proposed by the NIHR and we aim to publish the findings in high quality peer-reviewed open access (via Pubmed) journals. This will secure a searchable compendium of these publications and make the results readily accessible to the public, health care professionals and scientists. A final report will also be published in the NIHR EME journal.

The results of the study will also be disseminated through conferences at national and international ophthalmic meetings. As part of our commitment to PPI, we will hold a seminar for PPI representatives and other stakeholders to present the study findings. A lay person's summary will also be sent to patient support groups e.g. the Macular Society. This may be published in the Macular Society quarterly publication for the Lay Public. Following peer-reviewed publication, appropriate key findings, presentations and summaries will be made available on the study website. The Royal National Institute for the Blind (RNIB) Northern Ireland Branch has also indicated it's support for the study (personal communication with [name], Chief Executive) and will publicise the study to their membership and partner branches in England, Scotland and Wales. With agreement of the funder, appropriate press releases will be prepared by institutional press offices and members of the research team.

13.2 Authorship Policy

An author will be considered to be someone who has made a substantive intellectual contribution to the study. All investigators, Trial Statistician and relevant members of the Trial Management Group will potentially be co-authors. Collaborators will be acknowledged.

13.3 Trial Registration

The trial will be registered with the International Standard Randomised Controlled Trial Number (ISRCTN) register.

13.4 Data Sharing Statement

Requests for data sharing will be reviewed on an individual basis by the CI and TMG.

14 APPENDICES

14.1 Appendix I: Endothelial Cell Density Reference Table

There is substantive evidence in the literature identifying the fact that in an otherwise healthy adult human eye, the minimum endothelial cell density required to sustain normal physiological functions and thus corneal transparency, is between 400 and 500 c/mm2. If we establish an arbitrary safety limit of acceptable loss down to a figure of three times this value (1500cells/mm²), then the maximum % cell loss that would be tolerable in all four age groups identified above would be: 40%, 38%, 32% and 21%. There is also now ample evidence in the literature that phaco-assisted cataract surgery with a PC implant results in less than 5% cell loss at the one year post op period. Results in the literature for predicted cell loss after implantation of telescopic implants has improved significantly as devices have evolved. Current estimates are now running at 20%. This being the case, we believe that by setting age related endothelial cell density to minimal pre implantation of device safety levels of 2600 (50-59 years of age), 2500 (60-69 years of age), 2300 (70-79 years of age) and 2000 (80-89 years of age) (within the upper third of the normative range) we will provide a safety margin that will protect against decompensation both at time of surgery and into older life.

Age (Yrs)	50-59	60-69	70-79	80-89
EC Density (Range) (cells/mm ²)	2100-2900	2000-2800	1800-2600	1500-2300
EC Density (Mean) (cells/mm ²)	2500	2400	2200	1900

Adapted from: Ostern AE and Drolsum L. Corneal endothelial cells 6–7 years following cataract surgery in patients with pseudoexfoliation syndrome. Acta Ophthalmologica. 2012;90(5):408-411.

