	 Costs and cost-effectiveness To explore whether patient ocular parameters such as scar size, and volume at site are associated with visual outcome To assess the importance of Preferred Retinal Locus (PRL) and ocular dominance on outcomes. To evaluate the role of binocularity and visual summation on outcomes
Study Intervention	 (i) Interventional ARM: LMI-SI Lipshitz Macular Implant- Secondary Implant (OriLens) with tailored Low Vision Training (ii) Control ARM: Conventional Low vision training
Primary Outcome	Change in best corrected distance visual acuity (BCDVA) using number of letters improvement on Early Treatment Diabetic Retinopathy Study (ETDRS) Chart at 12 months
Key Secondary Outcomes	Change in best corrected near visual acuity (BCNVA) and reading speed at 12 months Vision-specific quality of life measured using the Impact of Vision Impairment Profile (IVI) at randomisation, and months six and 12 Health related quality of life status (EQ-5D-5L) at randomisation, months six and 12 Health service use and associated costs at months six and 12. Safety of device assessed by surgical complications at day 1, day 7, months one, three, six and 12 and endothelial cell density at baseline and at month 12.
Key Inclusion and Exclusion Criteria	 (i) Inclusion criteria Age 55 years or above Bilateral stable advanced AMD either neovascular (required to be stable for at least 12 months after last treatment) or atrophic AMD Bilateral uncomplicated cataract surgery with unifocal intraocular lenses Bilateral best-corrected distance visual acuity of 6/38-6/240 (LogMAR 0.80 to 1.60) Must demonstrate a 10-letter improvement in BCDVA (ETDRS chart) with the external x2.5 telescope in the eye for implantation Must have had experience of using low vision aids Have an endothelial cell density within normal limits for age Be willing to undergo laser capsulotomy in the eligible eye prior to randomisation (if required) Must be three months or more following any intraocular surgical or laser procedure Must be in good general health with every likelihood of involvement in the trial for the duration of the study and be able to physically or verbally complete the questionnaires Only one eye per participant will be included in the

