8.2.2 Inclusion Criteria

- Age 55 years or above
- Bilateral stable advanced AMD either neovascular (required to be stable for at least 12 months after last treatment) or atrophic AMD
- Bilateral uncomplicated cataract surgery with unifocal intraocular lenses
- Bilateral BCDVA of 6/38- 6/240 (LogMAR 0.80 to 1.60) and above
- Must demonstrate a 10-letter (0.20 LogMAR) improvement in BCDVA (ETDRS chart) with the external x2.5 telescope in the eye for implantation
- Must have had experience of using low vision aids
- Have an endothelial cell density appropriate for age as detailed in Appendix I
- Be willing to undergo laser capsulotomy in the eligible eye prior to randomisation (if required)
- Must be three months or more following any intraocular surgical or laser procedure
- Must be in good general health with every likelihood of involvement in the trial for the duration of the study and be able to physically or verbally complete the questionnaires
- Only one eye per participant will be included in the study.

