8.2.3 Exclusion Criteria

- Cataract surgery with multifocal intraocular lenses
- A history of glaucoma or of being on anti-glaucomatous medication
- Any other retinal condition
- Lack of clear view of the retina
- Abnormal or de-centred pupil
- Endothelial cell density <1500 cells/mm²
- History of ocular inflammatory disease
- Zonular instability or instability of existing intraocular lens
- BCDVA of better than 6/38 (0.80 LogMAR) or worse than 6/240 (1.60 LogMAR) in either eye
- Participants unable to provide informed consent
- Be in poor general health that could compromise attending follow-up assessments
- Difficulties with balance
- Not fluent in English*

* Fluency in English is required due to the complexity of screening examinations (reading speed is tested), the detailed explanations given for examinations and interventions, and the type of rehabilitation required.

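### The endothelial cell density entry criterion contradicts itself: the summary's normal limits and the Appendix I minima differ by 500 cells/mm², and no band covers age 90 and above

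*Protocol*

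**What the plan says.** Endothelial cell density enters eligibility in four places in the protocol.

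- **Section 1, Study Summary, inclusion:** "Have an endothelial cell density within normal limits for age". The only age-specific limits in the protocol are the ranges in the Appendix I table: 2100-2900 (50-59 years), 2000-2800 (60-69), 1800-2600 (70-79) and 1500-2300 (80-89), with means of 2500, 2400, 2200 and 1900.
- **Section 8.2.2, inclusion:** "Have an endothelial cell density appropriate for age as detailed in Appendix I".
- **Sections 1 and 8.2.3, exclusion:** "Endothelial cell density <1500 cells/mm²", at any age.
- **Section 14.1, Appendix I text:** "setting age related endothelial cell density to minimal pre implantation of device safety levels of 2600 (50-59 years of age"), and for the other bands "2500 (60-69 years of age), 2300 (70-79 years of age) and 2000 (80-89 years of age"). It places these levels in the upper third of the normative range.

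Appendix I also gives the reasoning. It adopts "an arbitrary safety limit of acceptable loss down to a figure of three times this value (1500cells/mm²"), says that the tolerable loss in the four age groups "would be: 40%, 38%, 32% and 21" per cent, and says of cell loss after telescopic implants "Current estimates are now running at 20" per cent. Section 8.2.2 sets a minimum age of 55 and no maximum.

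**The concern.** Appendix I holds two sets of figures: the ranges in its table and the minima in its text. Section 8.2.2 refers to the Appendix as a whole, and the summary's wording matches the ranges. Two sites could therefore classify the same eye differently, each following the protocol.

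This matters because specular microscopy is one of the tests that settle eligibility (section 8.7.2), and section 11.2 singles out endothelial damage as a potential risk of the device. Cell density is measured only at screening and month 12 (Table 2). In between, monitoring relies on corneal clarity. The baseline threshold therefore carries much of the protection.

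In addition, 1500 serves both as the pre-operative exclusion floor and as the limit for density after loss. Where it is the only floor in force, it leaves no room for loss.

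**Working it through.** **Inputs**, all from Appendix I: range, mean and minimum for each age band; a post-loss limit of 1500 cells/mm²; an expected loss of 20%.

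**1. The plan's own figure.** Tolerable loss = 1 − 1500 / pre-operative density. From the means:
- 1 − 1500/2500 = 40.0%
- 1 − 1500/2400 = 37.5%
- 1 − 1500/2200 = 31.8%
- 1 − 1500/1900 = 21.1%

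These round to the stated 40, 38, 32 and 21%. The figures are right, but they describe an eye at the age mean, not one at either entry floor.

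**2. Break-even density.** 1500 / (1 − 0.20) = 1875. Any eye admitted below 1875 ends under 1500 at the stated loss.

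**3. Each floor after 20% loss** (0.80 × density), with its tolerable loss in brackets:

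| Age | Lower normal limit | After loss | Appendix minimum | After loss |
|---|---|---|---|---|
| 50-59 | 2100 (28.6%) | 1680 | 2600 (42.3%) | 2080 |
| 60-69 | 2000 (25.0%) | 1600 | 2500 (40.0%) | 2000 |
| 70-79 | 1800 (16.7%) | 1440 | 2300 (34.8%) | 1840 |
| 80-89 | 1500 (0.0%) | 1200 | 2000 (25.0%) | 1600 |

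Under normal limits the shortfall covers 1800-1874 at age 70-79 and 1500-1874 at age 80-89. From age 90, with only the exclusion in force, it covers 1500-1874: 0.80 × 1500 = 1200. Under the minima no band falls short.

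**4. Sensitivity to the loss figure.** Break-even is 1667 at 10% loss, 1765 at 15%, 1875 at 20% and 2000 at 25%. At 10% or 15% the 70-79 lower limit stays above 1500 (1620 and 1530), and only the 80-89 band and ages 90 and above are exposed. The minima hold up to 25%.

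**5. The same eye under both rules.** A 75-year-old at 2000 lies inside 1800-2600 but below 2300: eligible by the summary, ineligible by the Appendix text. This holds whatever the loss figure.

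**6. Position of the minima.** Each range is 800 wide, and each minimum lies 500 above the lower limit: 500/800 = 62.5% of the range. The upper thirds start at 2633, 2533, 2333 and 2033, so each minimum is 33 short.

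**7. What the minima imply for screening.** Each lies 100 above its age mean. If densities are symmetric about the mean, more than half of each band fails. If they are also normal, the result depends on how many SDs the range of 800 spans:
- 2 SD: SD 400, z = 0.25, about 60% fail
- 4 SD: SD 200, z = 0.50, about 69% fail
- 6 SD: SD 133, z = 0.75, about 77% fail

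**The case against.** The strongest defence is that the main text has a natural reading. Section 8.2.2 sends the reader to Appendix I, whose text names only one set of pre-implantation thresholds; the table is labelled simply as range and mean, and the summary line is a loose abbreviation. On that reading every eye admitted at ages 55-89 keeps at least 1600 after a 20% loss. This is plausible, but section 8.2.2 does not say it, the summary says something else, and ages 90 and above remain without a band. The eligibility checklist is not shown and may settle the figures.

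Several stronger readings are tempting, and the documents do not support them.

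- **Three rival floors.** A reader might count the exclusion below 1500 as a third competing rule. Inclusion and exclusion criteria apply jointly, so if the minima govern, the exclusion is merely redundant at ages 55-89.
- **A general safety breach.** The shortfall needs the normal-limits reading and then affects only the lower end of the two oldest bands, plus ages 90 and above under the 1500 floor. The protocol itself calls 1500 arbitrary, and 1200 is still above the 400-500 it gives as the physiological minimum. The 20% refers to telescopic implants generally, and section 5.3 reports smaller loss with this device than with others.
- **A recruitment plan shown to fail.** A reader might convert the minima into a number to be screened. Appendix I does not say what its range represents, and the protocol gives recruitment counts but no screening forecast. The internal pilot in section 11.2 tracks the percentage randomised of those screened, so a low yield would become visible.
- **Bias in the treatment comparison.** Eligibility is settled before randomisation, so the ambiguity does not bias the comparison of the arms.

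**Conclusion.** The contradiction is real. For each age band the summary and the Appendix text set entry floors 500 cells/mm² apart, section 8.2.2 does not choose between them, and ages 90 and above have no age-specific figure. This needs no assumption beyond taking the Appendix table as the normal limits, and the protocol offers no other.

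The safety consequence is conditional. Given the Appendix's 20% loss and 1500 limit, it arises only on the normal-limits reading at 1800-1874 (age 70-79) and 1500-1874 (age 80-89), and from age 90 where 1500 is the only floor. The two younger bands are unaffected, and no band is affected under the minima.

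The recruitment consequence is also conditional. If the minima govern, and if people screened resemble the table and densities are roughly symmetric, more than half of each band would fail this criterion. The 60-77% range further assumes normality and a range spanning 2 to 6 SD. The upper-third discrepancy is small and changes no threshold.

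**What to change.** - Reconcile the summary's inclusion and exclusion lists, sections 8.2.2 and 8.2.3, and Appendix I into one unambiguous criterion covering every eligible age, including 90 and above. Repeat it identically in each place and on the eligibility checklist. Which floor applies is a clinical decision for the sponsor and is not proposed here.
- Correct the upper-third description in Appendix I so that it agrees with the figures beside it.
- If the minima are kept, note that they lie 100 cells/mm² above each age mean, and check recruitment feasibility against the expected failure rate on this criterion. The protocol has no numeric screening forecast, so this would be a new statement rather than a revision.

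The cost is a text amendment and a checklist update, and possibly a less favourable view of how many people must be screened to reach 132.
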